2 BACKGROUND AND RATIONALE OF STUDY

The incidence of Large Vessel Acute Ischemic Stroke (AIS) has been estimated to be approximately 250,000 patients per year in the United States and is the leading cause of disability and fifth leading cause of death. Although endovascular interventions (stentriever) and pharmaceutical (tPA) treatments exist for large vessel occlusion (LVO), their use is limited due to the short time window from symptom onset during which these treatments are indicated to be administered. Moreover, recent estimates suggest only approximately 10% of eligible patients receive interventional treatment which has shown to lead to better outcomes in several world-wide RCTs. Currently, the gold standard for stroke diagnosis is CT angiogram (CTA) which is limited to in-hospital use or a low number of mobile stroke ambulances, all costing multi-millions of dollars, requiring expert operators and IV injection of iodine-rich contrast material. Additionally, the clinical stroke assessment scales (RACE, LAMS, CPSS) used in the field, although low cost and non-invasive, have proven unreliable due to training requirements and low inherent accuracies, with SEN and SPE ranging in a recent study from 0.50-0.64 and 0.83-0.92, respectively[13,14]. In order for intervention to be successful, a standardized, quantitative, field based (prehospital and pre-CTA) diagnostic tool is needed to improve LVO identification and ensure rapid transfer to a capable medical facility.

Goals. Establish clinical viability of a fully automated, non-invasive transcranial Doppler (TCD) derived biomarker based on cerebral hemodynamics for prehospital LVO assessment.

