4.2 Study Endpoints

4.2.1 Phase 1 Study Endpoints

Phase 1 Primary Endpoint:

- Area Under the Curve (AUC), Sensitivity, and Specificity of VCI when compared against standard of care CTA imaging for large vessel occlusion assessment.

Phase 1 Secondary Technical Efficacy Endpoint:

- Area Under the Curve (AUC), Sensitivity, and Specificity of a novel machine learning (ML) algorithm when compared against standard of care CTA imaging for large vessel occlusion assessment.
- VCI and experimental ML algorithm compared to prehospital/neurological clinical scales for alternative diagnostic criteria.

Phase 1 Primary Safety Endpoint:

- Incidence of device-related serious adverse events
- Last Known Normal (LKN) to First Hospital Arrival (Initial Door-In) time
- Door to Initial CT imaging (non-contrast) time
- Door to IV-tPA time
- Door to Initial CTA Acquisition time
- Door to Groin Puncture time
- CTA Acquisition to Groin Puncture time

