4.15 Schedule of Assessments

Assessments	Phase 1 & 2 Schedule of Assessments			
	Cohort A¹ LVO TCD	Cohort B² Non-LVO TCD	Cohort C³ LVO NO TCD	Cohort D³ Non-LVO NO TCD
Informed Consent	X	X	X	X
Medical History	X	X	X	X
NIH Stroke Scale♦	X	X	X	X
Non-Contrast CT♦	X	X	X	X
CT Angiography♦	X	X	X	X
Cohort Assignment	X	X	X	X
Randomization TCD / No TCD	X	X	X	X
TCD Scan (NovaGuide or Lucid)	X	X		
Device-Related Adverse Events	X	X		
Concomitant Medications	X	X		

♦ Standard of Care

4. Cohort A LVO TCD subjects scans will be collected following CTA within a three (3) hour window, prior to treatment (e.g. mechanical thrombectomy).

5. Cohort B Non-LVO TCD subjects scans will be collected within a 24-hour period after enrollment.

6. If randomized to 'No TCD' group in either Cohort, TCD scan will not be conducted, but still followed through to discharge.

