11 STATISTICAL ANALYSIS

11.1 Phase 1 Statistical Analysis:

Primary Endpoint Analysis: Demonstration of VCI diagnostic performance at or exceeding 85% ROC-AUC (targeting SEN greater than 90%) to standard of care imaging.

Biomarker Validation and Analysis: VCI will be computed for each subject according to the procedure outlined in section 3.5, and group differences will be assessed using appropriate statistical methods. ROC-AUC will be computed detailing separability between groups for comparison to standard of care imaging (CTA) and prehospital/neurological clinical scales, along with SEN, SPE, and accuracy at various levels of diagnostic threshold, including that corresponding to Youden's maximal J-statistic.

Sample size calculation: From the results of our feasibility study, we estimate that expected effect size between VCI distributions for LVO (cohort A) and IHC groups (cohort B) will be large (Cohen's $D > 1.25$), such that only a small number of subjects in each group ($N = 11$) will be sufficient to detect significant differences (alpha of 0.05) with standard statistical power of 80%. However, in Phase 1 we seek to demonstrate the stronger aim of biomarker diagnostic performance in excess of 85% ROC-AUC. Assuming this target AUC is met, then sample size determines the confidence bounds on that estimate. In Phase 1 we require a sample of sufficient size to power confidence in the superiority of VCI diagnostic performance relative to current clinical prehospital stroke assessment scales. As existing preclinical scales top out at 78% AUC, this can be accomplished with a sample of roughly 50 subjects in each patient group, which gives a one-tailed 95% confidence bound on the target 85% AUC of less than 7%. The specification of 54 subjects per group is a target number intended to guarantee acquisition of a sufficient sample assuming at least 90% of target enrollment.

Initial safety endpoint analysis: Throughout the study we will collect adverse events, which will be used to determine the safety of the device within the acute stroke environment. In our EXPEDITE study which is also run in the ER for stroke assessment, the device has been designated minimal risk by the IRB and we have not had any serious adverse events in over 80 subjects. We will continue to closely monitor this metric.

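### Phase 1 rests its superiority rationale on clearing an uncited 78% AUC treated as error-free, while the planned comparison with scales has no stated test, no part in the sizing and only NIHSS scheduled

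*Combined protocol and SAP*

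**What the plan says.** All references are to the combined protocol and SAP.

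- **Primary criterion (11.1).** "Demonstration of VCI diagnostic performance at or exceeding 85% ROC-AUC (targeting SEN greater than 90%) to standard of care imaging". This is a criterion against CTA; the scales do not enter it.
- **Sizing (11.1).** The sample must be large enough to give confidence that VCI is superior to current prehospital scales. The argument is: "As existing preclinical scales top out at 78% AUC, this can be accomplished with a sample of roughly 50 subjects in each patient group". At that size, the plan says, the lower one-sided 95% limit lies within 7 percentage points of an AUC of 85%. The target of 54 per group allows for reaching 90% of enrolment. No source, scale name or standard error is attached to the 78%.
- **Comparison with scales (4.2.1, repeated for Phase 2 in 4.2.2).** A secondary endpoint reads "VCI and experimental ML algorithm compared to prehospital/neurological clinical scales for alternative diagnostic criteria". Section 11.1 also says that AUC will be computed for comparison with such scales. Neither place names a test, a pairing or a scale.
- **Data collected.** The only scale in the schedule (synopsis and 4.15) is "NIH Stroke Scale", marked as standard of care for all four cohorts. Section 4.18 adds an undefined entry for clinical assessment metrics. RACE, LAMS and CPSS appear only in section 2, "with SEN and SPE ranging in a recent study from 0.50-0.64 and 0.83-0.92, respectively".

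**The concern.** The stated reason for about 50 per group is superiority over existing scales. What the sizing delivers is a confidence bound for one AUC set against a constant. Those are different claims for two reasons.

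First, the 78% is itself an estimate from somewhere, but it is given no uncertainty.

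Second, it comes from outside this study. Sections 4.6.1 and 4.6.2 enrol CTA-defined LVO and non-LVO cohorts of equal size, and the non-LVO cohort excludes occlusions in a long list of vessels. That selection can move a scale's AUC as well as VCI's, in a direction the documents do not let us predict. Only a comparison in the same subjects removes the problem.

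The comparison that could do this is listed but cannot be carried out as written for the scales VCI is meant to improve on, because no prehospital scale is committed to collection. Eligibility requires CTA confirmation, so a scale first scored after enrolment would be scored with the CTA result available. A score not recorded before CTA cannot be recovered later without that risk of bias.

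**Working it through.** **Inputs.** From 11.1: VCI AUC 0.85, scale AUC 0.78, about 50 per group, one-sided 95% (z = 1.645). The correlation r between the two AUC estimates is not given; it is assumed and varied from 0 to 0.7.

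**Step 1: the plan's own figure.** Hanley-McNeil variance with m = n = 50: [A(1−A) + (m−1)(Q1−A²) + (n−1)(Q2−A²)]/(mn), where Q1 = A/(2−A) and Q2 = 2A²/(1+A).

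- A = 0.85: Q1 = 0.7391, Q2 = 0.7811, A² = 0.7225. The variance is (0.1275 + 49×0.0166 + 49×0.0586)/2500 = 0.001525, so SE = 0.0391.
- Half-width = 1.645 × 0.0391 = 0.064. Lower bound = 0.85 − 0.064 = 0.786.

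The claim of less than 7 points reproduces. It also holds at 49 per group, about 90% of 54 (half-width 0.0649), and at 54 (0.0618).

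**Step 2: power against a fixed 0.78.** The bound assumes that the observed AUC equals 0.85. If the true AUC is 0.85, power = Φ(0.07/0.0391 − 1.645) = Φ(0.15) = 56% at 50 per group. With the SE taken under the null instead (0.0464 at A = 0.78), it is 44%.

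**Step 3: the scale estimated in the same subjects.** SE(diff) = √(s₁² + s₂² − 2r·s₁·s₂), with s₁ = 0.0391 and s₂ = 0.0464. At r = 0 this is √(0.001525 + 0.002149) = 0.0606. Power = Φ(0.07/SE(diff) − 1.645).

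| Assumed r | SE(diff) | One-sided half-width | Power, 50 + 50 | n per group for 80% power |
|---|---|---|---|---|
| 0 | 0.061 | 0.100 | 31% | 230 |
| 0.3 | 0.051 | 0.084 | 39% | 162 |
| 0.5 | 0.043 | 0.071 | 49% | 117 |
| 0.6 | 0.039 | 0.064 | 56% | 95 |
| 0.7 | 0.034 | 0.056 | 67% | 72 |

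**Step 4: break-even points.**

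- An observed difference of 0.07 excludes zero when SE(diff) < 0.07/1.645 = 0.0426. This gives r > (0.003674 − 0.001811)/(2 × 0.0391 × 0.0464) ≈ 0.51.
- The paired analysis is as precise as the fixed benchmark when SE(diff) = 0.0391, that is r ≈ 0.59.

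**The case against.** The strongest reply is that this is an under-specified secondary analysis in a phase labelled feasibility, and that the plan claims less than it may seem to. Much of that stands.

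- **A reader might infer that the benchmark replaces an in-study comparison.** It does not. Sections 4.2.1 and 11.1 both list a comparison with clinical scales. The gap is in its specification and in its absence from the sizing.
- **A reader might infer that the plan would declare VCI superior once the bound clears 78%.** No such rule exists. The Phase 1 criterion is AUC of at least 85% against CTA, the 78% appears only in the sizing paragraph, and Phase 2 (11.2) does not use it. Nor does the plan state any power for VCI against scales; its only power figure (80%, N = 11) concerns the group difference in VCI.
- **A reader might infer that no comparator is available.** NIHSS is scheduled in all cohorts and entered at randomization (4.9), and it fits the neurological half of the endpoint's wording. The undefined entry in 4.18 might cover more, but it commits sites to nothing.
- **A reader might infer that the precision is overstated in any case.** That depends on r. From about 0.59 upward the paired analysis is at least as precise as the fixed benchmark.
- **A reader might try to derive the scales' true AUC, or the origin of 78%, from section 2.** It happens that (0.64 + 0.92)/2 = 0.78, but the documents do not say that this is the source. They also do not say how the sensitivities and specificities pair. A binormal conversion gives about 0.75 to 0.89 depending on the pairing, so the documents do not show that the scales exceed 0.78.

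What the reply does not answer is that superiority is the stated reason for the sample size, and nothing in the plan as written supports that inference.

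**Conclusion.** The concern holds as a gap between rationale and method. The bound in 11.1 is computed correctly, but it supports only a statement about VCI against an external 78%. It does not support superiority over scales in these subjects, and no prehospital scale is committed to collection.

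At 50 per group and true AUCs of 0.85 and 0.78, paired power is 31% to 67% over r = 0 to 0.7, and about 56% even against the fixed value. These figures rest on the Hanley-McNeil variance, equal groups and an assumed r. They do not affect the Phase 1 criterion of 85% AUC against CTA or the Phase 2 sizing. The point should be settled before enrolment, because scores not recorded before CTA cannot be obtained later free of knowledge of the CTA result.

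**What to change.** 1. In 11.1, specify the superiority comparison as a one-sided paired DeLong test of VCI against NIHSS in the TCD subjects, using an NIHSS recorded before CTA. The schedule does not state that timing, so it should be added.
2. Apply the same test to any prehospital scale already in the EMS or ED record. Name the scales and add a schedule and CRF row. The documents do not say how often such scores exist, so the number of subjects with both measures should be reported. A result against NIHSS alone should not be described as superiority over RACE, LAMS or CPSS.
3. Describe 78% as an external performance goal and cite its source.
4. Restate the sizing paragraph as a precision statement against that goal, and show the paired half-width over a range of r, instead of saying that about 50 per group delivers superiority.

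The cost is SAP wording, one schedule and CRF row, and some record abstraction. The stated precision becomes less favourable unless r is about 0.59 or more. No increase in sample size is needed if the claim is reduced to precision against the goal. If paired superiority with 80% power is wanted, the last column of the table gives the numbers needed.

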4.2.2 Phase 2 Study Endpoints

Phase 2 Primary Endpoint:

- Area Under the Curve (AUC), Sensitivity, and Specificity of VCI when compared against standard of care CTA imaging for large vessel occlusion assessment.

Phase 2 Secondary Technical Efficacy Endpoint:

- Area Under the Curve (AUC), Sensitivity, and Specificity of a novel machine learning (ML) algorithm when compared against standard of care CTA imaging for large vessel occlusion assessment.

- VCI and experimental ML algorithm compared to prehospital/neurological clinical scales for alternative diagnostic criteria.

Phase 2 Primary Safety Endpoint:

- Incidence of device-related serious adverse events
- Last Known Normal (LKN) to First Hospital Arrival (Initial Door-In) time
- Door to Initial CT imaging (non-contrast) time
- Door to IV-tPA time
- Door to Initial CTA Acquisition time
- Door to Groin Puncture time
- CTA Acquisition to Groin Puncture time

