In this work, we will also measure “Get with the Guidelines, Stroke” metrics from each site and compare them to literature, national and site metrics. This will enable us to demonstrate that the system does not adversely affect standard of care for subjects suspected of stroke. The reason we believe it will not affect standard of care is because the device will be used after initial CT and IV-tPA is administered, while the subject is waiting for CTA or intervention. The time window, although short, is available to allow us to measure both the TCD waveform and CTA to confirm VCI is an effective biomarker. Additionally, the times will be compared against the randomized groups (Cohort C and D).

Door to diagnostic imaging. (Statistical demonstration that show we will not delay anything when adding our NovaGuide workflow to), e.g. “Get with the Guidelines, Stroke”: We will calculate the following for subjects that have NovaGuide measurements:

- IV rt-PA arrive by 2 hour, treat by 3 hour: Percent of acute ischemic stroke patients who arrive at the hospital within 120 minutes (2 hours) of time last known well and for whom IV t-PA was initiated at this hospital within 180 minutes (3 hours) of time last known well.
- % Door to CT \leq 25 minutes: Percent of patients who receive brain imaging within 25 minutes of arrival.
- Door to Puncture (DTP) Time within 90 minutes: (Percentage of patients with acute ischemic stroke who receive mechanical endovascular reperfusion)

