11.2 Phase 2 Statistical Analysis

Primary Endpoint Analysis: Demonstration of VCI biomarker performance at or exceeding 90% ROC-AUC (targeting SEN & SPE greater than 90%) to standard of care imaging across multiple centers.

Here, we will determine the final biomarker performance using the dataset collected and reviewed by the core lab. Similar analyses will be run on the VCI biomarker distributions for the Phase 2 subject group as was done in Phase 1. Additionally, subgroup analyses comparing biomarker results across research sites, and age groups, will be conducted to determine if any age or NovaGuide inter-operator variability effects are present in the data (two-way ANOVA with post-hoc comparisons).

Sample size calculation: In Phase 2, we seek to demonstrate stricter confidence bounds on biomarker diagnostic performance in excess of 90% ROC-AUC. Assuming the biomarker is observed to meet that performance threshold, then a sample of approximately 150 LVO subjects in each patient group is required to attain a one-tailed 95% confidence bound on the observed AUC of 3%. That is, the target AUC and sample size would afford 95% confidence that the underlying general population AUC is greater than 87%. Moreover, across five sites, this results in approximately 30 LVO subjects per site, affording sufficient power for detection of moderate potential inter-site effects in the range of Cohen’s $D \geq 0.75$.

Calculate study and site specific stroke workflow times: Stroke workflow parameters and times are well characterized in literature, including “Get with the Guidelines, Stroke” published by the American Heart Association, Inc. and will be utilized as a historical control comparator for data collected in Phase 2. We will use these published stroke guidelines which have mean times for the stroke workflow parameters to show that we are non-inferior to these when using the NovaGuide device. Additionally, the data will be compared to the corresponding randomized group (Cohort C and D)

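### Sections 11.1 and 11.2 build the no-delay demonstration on measures other than the workflow times listed in 4.2, and name no statistic for the randomised comparison of those times

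*Combined protocol and SAP*

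**What the plan says.** **Endpoints.** Sections 4.2.1 and 4.2.2 each list six workflow times under the Primary Safety Endpoint. They include "Door to IV-tPA time", "Door to Groin Puncture time" and "CTA Acquisition to Groin Puncture time". Neither section gives a unit, summary statistic, test or margin.

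**Phase 1 analysis (11.1).** The site metrics are to be compared with literature, national and site figures. One further sentence says the times will also be compared with Cohorts C and D. The part labelled a statistical demonstration then begins "We will calculate the following for subjects that have NovaGuide measurements" and lists three percentages:

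- tPA: "IV rt-PA arrive by 2 hour, treat by 3 hour: Percent of acute ischemic stroke patients who arrive at the hospital within 120 minutes" of last known well and "for whom IV t-PA was initiated at this hospital within 180 minutes (3 hours) of time last known well".
- Brain imaging within 25 minutes of arrival.
- Puncture: "Door to Puncture (DTP) Time within 90 minutes: (Percentage of patients with acute ischemic stroke who receive mechanical endovascular reperfusion".

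**Phase 2 analysis (11.2).** The lead analysis is non-inferiority against "published stroke guidelines which have mean times for the stroke workflow parameters". A comparison with Cohorts C and D is added, again without a statistic, test or margin.

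**Sequence.** Randomisation follows consent and CTA-confirmed eligibility (4.6, 4.9). The Cohort A scan takes place after CTA and before thrombectomy (4.16.2), with up to 20 minutes of set-up and search and up to 20 minutes of monitoring (4.16.1). Section 11.1 says the device is used after tPA has been given. Section 4.16.2 says only that tPA may come first.

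**The concern.** The endpoints are times, but the analysis that is spelled out uses percentages in Phase 1 and published means in Phase 2. Neither of these uses the randomised control, although the design provides one in the same hospitals. The percentages also leave out TCD-arm subjects scanned with the Lucid M1 alone.

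The tPA item measures something other than the listed endpoint, and the puncture item can be read in two ways. The interval that the Cohort A scan occupies has no metric in 11.1. At stake is whether the study can support its statement that scanning does not delay stroke care. A real delay could be missed, and the two phases could give different answers on endpoints that 4.2 words identically.

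**Working it through.** The plan states no power, margin or alpha for the workflow times, so there is no figure of its own to reproduce.

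**1. What the tPA percentage measures (documents only).** A subject counts if arrival is at most 120 minutes after last known well, and passes if tPA starts by 180 minutes. The passing limit on door-to-tPA time is therefore 180 minus arrival time:

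| Arrival after last known well (min) | Longest passing door-to-tPA time (min) |
|---|---|
| 0 | 180 |
| 30 | 150 |
| 119 | 61 |
| 120 | 60 |

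A subject arriving at 30 minutes passes after 150 minutes in hospital, while one arriving at 119 minutes fails at 62. Anyone arriving after 120 minutes is not counted.

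**2. Which listed times a scan can affect (documents only).** Arrival, initial CT and CTA all precede randomisation, because eligibility needs CT and CTA findings. Three of the six times are therefore fixed before allocation, and so is the imaging percentage in 11.1. Door to tPA is exposed only where tPA follows randomisation. Door to puncture and CTA to puncture are clearly exposed in Cohort A. The stated maxima allow a session of 20 + 20 = 40 minutes.

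**3. The puncture item.** The heading sets a 90-minute limit. The bracket describes the share of ischemic stroke patients who receive reperfusion, with no time in it. These are different numerators, and possibly different denominators.

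**4. Size for puncture (assumed inputs).** The documents give no time distributions. Assume log-normal door-to-puncture times with log-SD 0.4, a 20-minute delay in every TCD subject, 54 punctured per arm (the full Phase 1 Cohort A arm) and a one-sided 5% level. The percentage within 90 minutes is Φ(ln(90/median)/0.4) without delay and Φ(ln(70/median)/0.4) with it, because 90 − 20 = 70.

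| Median (min) | % within 90, no delay | % within 90, delayed | Power, percentage | Power, log minutes |
|---|---|---|---|---|
| 70 | Φ(0.628) = 73.5 | Φ(0) = 50.0 | about 80% | about 98% |
| 90 | Φ(0) = 50.0 | Φ(−0.628) = 26.5 | about 81% | about 91% |
| 130 | Φ(−0.919) = 17.9 | Φ(−1.548) = 6.1 | about 60% | about 69% |

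Power is by simulation (two-proportion z-test against t-test on log minutes) and is good to about one point.

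**5. Size for tPA (assumed inputs).** Assume arrival uniform from 20 to 120 minutes, door-to-tPA log-normal with log-SD 0.4 and median 45, 60 or 75 minutes, the same 20-minute delay, and all 54 per arm eligible and treated. The tPA percentage falls from 96/88/76% to 88/74/60%. Power is 48–56% on the percentage against 98–100% on log minutes. This holds only for subjects randomised before tPA.

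**6. Sensitivity to the choice of time statistic.** With untransformed means, a 15-minute delay, two-sided 5% and CV 0.4, power at a 90-minute puncture median is 49% (percentage) against 52% (mean) with 54 per arm. At a 110-minute median and CV 0.5 it is 31% against 24%. The advantage of times therefore depends on handling skewness, for example by logs or ranks.

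**The case against.** The best defence is that the percentages are benchmark figures for comparison with outside data, and that 11.1 and 11.2 separately plan a comparison with Cohorts C and D. In 11.1 that comparison is on times. On this reading the plan already contains the right contrast. The tests simulated above compare the percentages between arms, which 11.1 does not propose. In addition, 11.1 places the scan after tPA, so most tPA times could not be affected. If only 10–20% of subjects could be delayed (an assumption, at a 60-minute median and 54 per arm), power on door-to-tPA minutes would itself be only about 10–20%. The puncture wording may just be loose, and a time endpoint can properly be summarised as a proportion within a limit.

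Much of this stands. A reader might infer that the percentages are the only reported result, or that a real delay would leave them almost unchanged. The documents do not support the first, because both sections mention the randomised cohorts. The second fails on the figures above: the tPA percentage falls by 8 to 16 points and the puncture percentage by 12 to 24. Nor does 4.2 state that the endpoints are in minutes.

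What the defence does not answer is that the randomised comparison is a single added sentence in each section with no statistic, while the detail goes to measures that do not match 4.2. The tPA mismatch needs no assumption. The statements on whether tPA comes before the scan differ between 11.1 and 4.16.2 and must be reconciled.

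**Conclusion.** The point holds as a mismatch between listed endpoints and spelled-out analysis. The tPA percentage is not door-to-tPA time, the puncture item is internally inconsistent, CTA to puncture has no named metric in 11.1, and the randomised comparison is left unspecified in both phases.

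The consequence is some loss of ability to see a delay. For a 90-minute puncture cut-off it is moderate: about 18 points of power at a 70-minute median (98 − 80) and 9 at 130 (69 − 60). It is larger for tPA, but only for subjects randomised or scanned before tPA, who may be few. Both figures rest on assumed log-normal times, a uniform 20-minute delay and full use of 54 per arm. With untransformed means the advantage can shrink or reverse. The definitional findings rest on the documents alone.

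This is a clarification that should be made. It does not invalidate the design.

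**What to change.** In 11.1 and 11.2:

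- Make the comparison of the 4.2 times between the randomised TCD and No TCD arms the named no-delay analysis in both phases, on the log scale or by a rank-based method. The main items should be CTA to puncture and door to puncture in Cohort A against Cohort C.
- Report the estimated difference with its confidence interval. If the claim is to be non-inferiority, state and justify a margin, since the documents give none.
- Report how many subjects in each arm were punctured, because these times exist only for them.
- Keep the Get With The Guidelines percentages and the published means as descriptive benchmarks.
- Reword the puncture item as the percentage of punctured subjects with door-to-puncture time within 90 minutes.
- Reconcile 11.1 and 4.16.2 on the order of tPA and scan.

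The cost is wording. Workflow times are already collected (4.18) and the randomised control already exists (4.9). The downside is that the benchmark figures lose their role as the demonstration.
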